1 INTRODUCTION

Toric soft contact lenses work best for people with astigmatism and other refractive errors (e.g., nearsightedness, farsightedness). The use of toric soft contact lenses has increased significantly in recent years. Recently released data on prescription habits with soft toric lenses ranged from 13% to 59%. Soft toric contact lens wearers demand two things from their contact lenses, great comfort and excellent vision.

Contact lens manufacturers are continuously innovating in this area, with increased availability of soft toric contact lenses with novel designs in a range of replacement frequencies, from daily disposables to monthly replacement, and different materials, including silicone hydrogels.

Therefore, CooperVision is interested in comparing the short-term clinical performance and subjective acceptance of Proclear toric contact lenses (Lens A; Control) with Biofinity toric (Lens B; Test) silicone hydrogel lenses in a short-term, non-dispensing fitting study.

2 OBJECTIVES

To evaluate and compare the performance of Proclear toric (control) and Biofinity toric (test) contact lenses in existing soft toric lens (CL) wearers in a short term (15 minutes wear) study.

The primary outcome variable for this study is:

- Overall fit acceptance

3 HYPOTHESIS

Null Hypothesis (H₀) There is no difference in overall fit acceptance between the study lenses.

Alternative Hypothesis (H₁) There is a difference in overall fit acceptance between the study lenses.

4 MATERIALS AND METHODS

4.1 STUDY DESIGN

4.1.1 OVERALL DESIGN

This is a prospective, participant masked, bilateral eye, non-dispensing cross-over study with 3 study visits that will be conducted on 2 separate days. The consent, screening and lens fitting assessments will be done on study day 1 (Visit 1) to determine eligibility and confirm optimal contact lens powers. The performance of both lens types during bilateral wear will be assessed on study day 2, with a cross-over from Lens A (Visit 2) to Lens B (Visit 3). Participants will exit the study at the end of V3.

4.1.2 RANDOMIZATION

There is no randomization in this study. Each participant will wear each of the two lens types for approximately 15 minutes during the assessment visits. Each participant will wear the Proclear toric lens first (Visit 2) and the Biofinity toric lens (Visit 3) second.

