4.1.3 MASKING

[figure not shown]
The order of contact lens wear will be masked to the study participants only. The lenses will be removed from their blister pack by an assistant and transferred to an unmarked lens case to maintain participant masking of the study lenses. Participants will then be instructed to remove the lenses from the lens case and insert them onto their eyes. It is not possible for the study investigators to be masked because of the plan for a fixed lens order.

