4.4.1 SCREENING (V1)

A documented informed consent process will be conducted with all participants prior to their enrolment in the study and prior to any data collection or measurements. All participants who sign the informed consent letter will be assigned a study ID number. The investigator will determine participant eligibility using the inclusion and exclusion criteria. Ineligible participants will be discontinued from the study. Participants will attend this visit wearing their spectacles.

Visit procedures (V1):

1. The participant will be required sign an Informed Consent Form prior to enrollment. When the participant has signed the consent form, the participant will be considered enrolled in the study.
2. Participant demographics and medical history (age, sex, medical conditions, medications, allergies).
3. Contact lens history (habitual lens information and wearing habits).
4. [REDACTED]
5. [REDACTED]
6. Full anterior ocular health examination (Including fluorescein; Efron scale).
7. Participant to insert LENS A [REDACTED] trial lens.

8. Allow 5 minutes settling time.

9. [REDACTED]

10. Measure lens fitting characteristics ([REDACTED]
overall fit acceptance).

11. Participant to remove LENS A and to insert trial toric LENS B [REDACTED].

12. Allow 5 minutes settling time.

13. [REDACTED]

14. Measure lens fitting characteristics [REDACTED]
overall fit acceptance).

15. Participant to remove LENS B.

16. The investigator will confirm that the participant meets the eligibility specifications set out
in the inclusion criteria and exclusion criteria and is eligible to continue in the study.

17. Instructions. The participant will be advised:

- To attend V2 with their habitual spectacles.
- That they are permitted to wear their habitual CLs every day from now on (end of
screening visit) until the day of V2 (i.e. no habitual CL wear on day of V2 visit).

18. Confirmation of final lens powers for LENS A & B. If final lenses for either lens type are
not in stock, lenses will be ordered.

[REDACTED]

[REDACTED]

[REDACTED]

[REDACTED]

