4.4.2 STUDY VISITS (V2 & V3)

Study visits 2 and 3 to be conducted on the same day, with both study lens types in the final lens power as determined during the screening visit required to be available on site. Participants will attend this visit wearing their **spectacles and not having worn their habitual CLs on the day of this visit.**

Visit 2 (LENS A) – Visit Procedures:

1. Changes in health & medications
2. Lens insertion

Part A – post-insertion measurements

3. [REDACTED]
- [REDACTED]
- [REDACTED]
- [REDACTED]
5. Lens fit assessment
 - [REDACTED]
 - [REDACTED]
 - [REDACTED]
 - [REDACTED]
 - Overall fit acceptance (0 – 4) and reason if Grade 2 or less.

Part B – 15 minutes-post insertion measurements

6. [REDACTED]
- [REDACTED]
- [REDACTED]
- [REDACTED]
- [REDACTED]
8. Lens fit assessment
 - [REDACTED]
 - [REDACTED]
 - [REDACTED]
 - [REDACTED]
 - Overall fit acceptance (0 – 4) and reason if Grade 2 or less.
9. Lens removal
10. [REDACTED]
- [REDACTED]

Visit 3 (LENS B) – Visit Procedures:

1. Lens insertion

[figure not shown]
Part A – post-insertion measurements

2.

4. Lens fit assessment

➤

➤ Overall fit acceptance (0 – 4) and reason if Grade 2 or less.

Part B – 15 minutes-post insertion measurements

5.

7. Lens fit assessment

➤

➤ Overall fit acceptance (0 – 4) and reason if Grade 2 or less.

8. Lens removal

9.

10.

11.

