10 STATISTICAL ANALYSIS AND DATA MANAGEMENT

10.1 STATISTICAL ANALYSIS

All data will be analysed by CORE at the University of Waterloo. Unmasked data analysis will be conducted using Statistica and / or SPSS, or other appropriate software. Descriptive statistics will be provided on information regarding baseline variables (age, sex, etc.). Table 6 lists the primary outcome variables and anticipated statistical procedures. [REDACTED]

[REDACTED]. The OD data will be analysed for certain assessments that are conducted for each eye separately, for example [REDACTED] lens fit.

Table 6:Statistical procedures

Variable	Analysis	Statistical test
Lens Fit assessments	
Descriptive and other statistics
 
Effect of treatment on outcome variable within subjects (comparison between study lenses) Effect of time on ratings (comparison over time)
	
Mean, Median*, Standard Deviation, Minimum, Maximum, Frequency count
 
Friedman Wilcoxon matched pairs test Paired t-test

A binomial test will be used to analyze the results for the count data of subjective preferences.

Where relevant, the number of “no preference” responses will be evenly distributed to the two options on the basis they would be equally likely to choose either.

The final study report will include a table that lists the final lens prescription for the two lens types by participant, in order to determine the count and percentage of matching prescriptions between both lens types.

No analysis will be conducted on biomicroscopy data as this is only collected for safety purposes.

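### Every participant wears Proclear first and Biofinity second, so the planned comparison mixes the lens effect with the order effect and cannot by itself test the lens hypothesis

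*Combined protocol and SAP*

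**What the plan says.** Section 3 states the alternative hypothesis as "There is a difference in overall fit acceptance between the study lenses". Section 4.1.1 describes a one-way design, "with a cross-over from Lens A (Visit 2) to Lens B (Visit 3"), on a single study day. Section 4.1.2 says there is no randomisation and that "Each participant will wear the Proclear toric lens first (Visit 2) and the Biofinity toric lens (Visit 3) second".

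Table 6 in section 10.1 lists the between-lens analysis as "Effect of treatment on outcome variable within subjects (comparison between study lenses"), using Friedman, Wilcoxon matched pairs and paired t-tests. The readable text has no period or order term and does not state that the order effect is taken to be zero.

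Section 4.1.3 masks participants only and explains: "It is not possible for the study investigators to be masked because of the plan for a fixed lens order". The screening fits in section 4.4.1 follow the same order ("Participant to remove LENS A and to insert trial toric LENS B"), so the study collects no Biofinity-then-Proclear data at any visit.

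**The concern.** A paired test answers the question in section 3 only if being worn second has no effect on the fit grade. If it has one, a significant result could come from order alone, and a null result could be a real lens difference cancelled by order. The alpha of 0.05 and the power of 84% in section 4.2.1 apply to the lens question only under that assumption. The study cannot test it, because nobody wears Biofinity first.

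There is a separate, secondary point. The investigators know which lens is on the eye and apparently give the primary grade, although section 4.6.5 does not name the grader. A grading bias that follows the lens is a different problem from order, and randomising the order would not remove it.

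**Working it through.** **Inputs.** From section 4.2.1: 37 completers, difference 0.42, alpha 0.05 (taken as two-sided, since section 3 gives no direction), power 84%, paired t-test. From section 4.2.2: up to 40 participants dispensed lenses. The standard deviation (SD) of the paired differences is not in the readable text, so it is back-solved, with 0.60 to 1.00 as an assumed range. The order effects of 0.1 and 0.2 grade are also assumed.

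**Step 1: the plan's own figure.** Paired t-test power comes from the non-central t distribution with 36 degrees of freedom and non-centrality (difference / SD) × √37. Setting power to 84% at 0.42 gives SD = 0.841. Because the SD is not readable, this shows what the figure of 37 implies and does not verify it independently. SD 0.84 is used below (power 84.1%).

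**Step 2: what is estimated.** Write τ for the lens effect, π for the second-minus-first order effect, and λ for carryover from the first lens.

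- Proclear then Biofinity: expected B−A difference = τ + π + λ(A)
- Biofinity then Proclear: expected B−A difference = τ − π − λ(B)

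The plan has only the first line: one equation and more than one unknown. A larger sample, a covariate or a different test does not change that. With both sequences, the average of the two lines is τ + [λ(A) − λ(B)]/2, and π drops out.

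**Step 3: fixed order, n = 37.** The standard error at SD 0.84 is 0.84/√37 = 0.138. In the last row the net shift is 0.42 − 0.20 = 0.22.

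| Situation | SD 0.60 | SD 0.84 | SD 1.00 |
|---|---|---|---|
| No lens effect, order effect 0.1: rejection | 17% | 11% | 9% |
| No lens effect, order effect 0.2: rejection | 51% | 29% | 22% |
| Lens effect 0.42, no order effect: power | 99% | 84% | 70% |
| Lens effect 0.42, opposing order effect 0.2: power | 58% | 34% | 26% |

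**Step 4: both orders, period-adjusted.** The standard error is (SD/2) × √(1/n₁ + 1/n₂), with n₁ + n₂ − 2 degrees of freedom.

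- Power at 0.42 and SD 0.84: 84.0% at 18/19, 82.7% at 15/22, and 86.9% at 20/20. With the unrounded SD of 0.8414, 18/19 gives 83.9% and the smallest total reaching 84% is 38, within the planned 40.
- Simulated false-positive rate with an order effect of 0.2 and no lens effect: 5% at all three SDs.
- Simulated power at 0.42 with an opposing order effect of 0.2: 98%, 84% and 70% across the three SDs.

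**Step 5: what randomising the order does not solve.**

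- A lens-linked grading shift of 0.2 with no lens effect gives 29% false positives under either design at SD 0.84 (about 50% at SD 0.60 and 22% at SD 1.00).
- Carryover of 0.2 from Proclear only leaves a bias of 0.2/2 = 0.1 grade and 11% false positives, against 29% in fixed order (SD 0.84).

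**Step 6: whole grades.** A simulation used rounded grades limited to 0–4, with an assumed latent mean of 3.0, a realised SD of 0.83 and a realised order shift of 0.21. Fixed order rejected 32% (paired t) and 31% (Wilcoxon). Both orders rejected 5.3% (t) and 5.0% (rank-sum). The result does not depend on treating the grade as continuous.

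**The case against.** The fixed order is openly stated and contradicts nothing else in the protocol. Several features make a large order effect less likely:

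- about 15 minutes of wear per lens;
- adapted toric wearers;
- fitting lenses not reused at study visits;
- no habitual lens wear on the day;
- a slit-lamp grade rather than a comfort rating.

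No mechanism has been shown by which a short wear of Proclear would change the later fit grade of Biofinity. The assumed shifts are not trivial either. If grades are whole numbers, 0.1 and 0.2 correspond to 37 × 0.1 = 3.7 and 37 × 0.2 = 7.4 net one-grade changes among 37 people. An order effect of 0.05 would give only 6.4% false positives at SD 0.84 (7.8% at SD 0.60, 6.0% at SD 1.00). The repeat grades within each wear period and the screening grades could also show drift.

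Most of this stands as a limit on how much bias to expect, and the point does not claim that the bias is large. It does not restore the lens inference: the within-wear and screening data all follow the same order, so they cannot separate lens from order. A rationale may sit in redacted text or in the missing figure, but it would not undo the confounding. The objection is also right that a change of design requires a matching edit to section 4.2.1 and a named time point for the primary comparison. Much of the visit procedure is redacted, so how easily the steps can be relabelled cannot be fully checked.

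**Conclusion.** The concern holds. That lens and order are confounded follows from the design and needs no assumed numbers; confidence in it is high. The size of any bias is unknown. The 11%, 29% and 34% figures rest on assumed order effects and a back-solved SD, and they show sensitivity, not expected harm. The grader-masking point is secondary and held with moderate confidence, because the grader is not named. This should be fixed before lenses are worn at Visit 2, since no later analysis can recover the missing sequence.

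**What to change.** **Preferred change: randomise the order.**

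- **4.1.2:** After eligibility is confirmed, randomise participants 1:1 to Lens A then Lens B, or Lens B then Lens A, at V2 and V3, from a blocked list held by the assistant who transfers the lenses.
- **10.1:** Define the primary lens comparison as the average of the mean B-minus-A differences in the two order groups. Name the time point (post-insertion or 15 minutes) and settle the test in advance. If a rank test is chosen, compare V2-minus-V3 differences between the order groups.
- **4.2.1:** Restate the sample size for this analysis.
- **4.1.1, 4.4, 4.4.2 and Table 3:** Revise the design description and the V2/V3 lens labels to match.
- **Section 12:** Define randomised as assigned a lens order. Study IDs are given at consent (section 4.4.1).
- **4.1.3:** Delete the fixed-order rationale, name the grader, and withhold lens identity from that person at V2/V3 where feasible. State that masking may be imperfect, because the lenses differ (Table 1) and both are graded in a known order at screening.

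**Cost.** A list and text edits. Lenses are already "removed from their blister pack by an assistant and transferred to an unmarked lens case to maintain participant masking", and section 4.4.2 already plans the day "with both study lens types in the final lens power as determined during the screening visit required to be available on site". No extra visits, participants or lenses are needed, and no extra staff on the assumption that the same assistant can track the order. The power cost is about 0.1 percentage point at 18/19 and 1.4 points at 15/22. Differential carryover and lens-linked grading bias would remain possible.

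**Fallback: keep the fixed order.** Give the reason. State in the hypothesis and conclusion that the result compares second-worn Biofinity with first-worn Proclear under unmasked grading and will not be attributed to the lens alone. This costs text only.

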4.1.3 MASKING

[figure not shown]
The order of contact lens wear will be masked to the study participants only. The lenses will be removed from their blister pack by an assistant and transferred to an unmarked lens case to maintain participant masking of the study lenses. Participants will then be instructed to remove the lenses from the lens case and insert them onto their eyes. It is not possible for the study investigators to be masked because of the plan for a fixed lens order.

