4.3.4 PRODUCT ACCOUNTABILITY

Accountability logs will be kept to include the number of lenses received, dispensed, unused and returned to sponsor (where relevant). All products dispensed to participants will be recorded in the study binder.

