4.4 SCHEDULED AND UNSCHEDULED VISITS

This study has a total of 3 study visits, including the screening visit. The involvement for each participant will be approximately 3.5 hours across two separate visits to CORE. A summary of the study visits is shown in Table 2.

Table 2: Summary of visits

Visit number	Visits	Visit length	Visit Window
1	Screening, Lens fit (both lens types), Eligibility. Study lenses order (if applicable)	1.75 hrs	n/a
2	Part A: Lens insertion (LENS A). [REDACTED] lens assessments Part B: 15 minute post insertion (LENS A). [REDACTED] lens assessments. Lens removal.	1.75 hrs	V2 & V3 to be conducted on the same day
3 & Exit	Part A: Lens insertion (LENS B). [REDACTED] lens assessments Part B: 15 minute post insertion (LENS B). [REDACTED] lens assessments. Lens removal. Exit assessments	3.5 hrs	n/a
Total		0.5 hrs	If applicable
Early Exit	If applicable (e.g. participant discontinued)		

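### The only primary outcome is a judgement grade, only participants are masked, and the one readable reason for leaving investigators unmasked is a fixed lens order that the plan itself chose

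*Combined protocol and SAP*

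**What the plan says.** Section 2 lists one primary outcome ("The primary outcome variable for this study is": overall fit acceptance). Section 4.6.5 defines it as a grade from 0 to 4 given at the slit lamp, with a verbal anchor for each grade and a reason to be recorded for grade 2 or below. At each of Visits 2 and 3 it is graded twice, after insertion and at 15 minutes (4.4.2). Neither 4.4.2 nor 4.6.5 names the person who grades.

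Section 4.1.2 states that there is no randomisation: "Each participant will wear the Proclear toric lens first (Visit 2) and the Biofinity toric lens (Visit 3) second". No reason for that order appears in the readable text. Table 2, Table 3 and section 4.4.2 label the visits by lens.

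On masking, section 4.1.3 says: "The order of contact lens wear will be masked to the study participants only". It then explains: "It is not possible for the study investigators to be masked because of the plan for a fixed lens order". The same section already provides a handling step for participant masking: "The lenses will be removed from their blister pack by an assistant and transferred to an unmarked lens case".

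The tests listed in section 10.1, Table 6 (Friedman, Wilcoxon matched pairs, paired t-test) include no term for order or visit.

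**The concern.** Masking the participant does not protect a grade that an observer assigns. Here the visit number alone tells the grader which lens is on the eye, and the grade is a judgement. The recorded reason for grade 2 or below gives some discipline at the lower end, but it does not touch the choice between 3 (imperfect but dispensable) and 4 (perfect).

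If the grader leans towards one lens, even slightly and without intent, the lean goes into the within-participant difference that the trial tests. The same holds for anything that changes between the first and second wearing period of the day. Lens and visit coincide in every participant, so no analysis of these data can take the components apart, and a larger sample would only estimate their sum more precisely.

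The readable text does not say that masking fails because the lenses look different or because staff are lacking. It gives only the fixed order, which the protocol is free to change.

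**Working it through.** **1. What the paired difference estimates.** Let L be the lens effect (B minus A), V the effect of second visit minus first, and G the net lean of the grader towards B. Ignore carry-over.

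- Fixed order, every participant: mean of (B − A) = L + V + G. One equation with three unknowns.
- Balanced random order: A-first participants give L + V + G and B-first participants give L − V + G. The average of the two is L + G.

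So randomising removes V but not G. It reduces G only if the grader is also kept unaware of the lens, which the random order makes possible.

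**2. The plan's own sample size.** Inputs from section 4.2.1: paired t-test, alpha 0.05, power 84%, difference 0.42 points, n = 37. The readable text gives neither the standard deviation (SD) of the differences nor the number of sides; section 3 states a non-directional alternative, so I take two sides. With df = 36 and critical value 2.028, power = P(|T| > 2.028), where T is noncentral t with noncentrality 0.42 × √37 / SD. Setting power to 0.84 gives SD = 0.841, that is 0.42/0.841 = 0.50 and noncentrality 3.04. Check: SD 0.84 gives n = 37 and power 84.1%. (A one-sided test would imply an SD of about 0.95.)

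**3. Effect of an assumed lean.** Set L = V = 0 and G = b, where b is the net shift in the mean after any loss at the scale maximum of 4. The noncentrality becomes b × √37 / SD; for b = 0.20, 0.20 × 6.083 / 0.841 = 1.45.

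| Assumed net lean b | b / 0.42 | p<0.05 at SD 0.841 | SD 0.6 | SD 1.0 |
|---|---|---|---|---|
| 0.05 | 12% | 6.4% | 7.8% | 6.0% |
| 0.10 | 24% | 10.8% | 16.7% | 9.1% |
| 0.20 | 48% | 29.1% | 50.5% | 22.0% |
| 0.30 | 71% | 56.0% | 84.1% | 42.7% |

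A simulation of 100,000 trials per cell agreed to within 0.2 percentage points. At SD 0.841 an observed mean difference of 2.028 × 0.841 / √37 = 0.28 points reaches significance.

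**4. Weight of the columns.** Only the SD of 0.841 reproduces the plan's 37. For a difference of 0.42 with 84% power, SD 0.6 would need about 20 participants and SD 1.0 about 52; with 37, power would be about 98.5% and 70%. Those two columns are sensitivity values only. The values of b are assumptions throughout, and only the paired t-test is modelled.

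**The case against.** The strongest reply is that this is a disclosed choice and not an error. Section 4.1.1 calls the study participant masked, sections 4.1.2 and 4.1.3 state the fixed order and its consequence openly, and this is a short, non-dispensing fitting study. That stands: the plan does not contradict itself here. But section 3 sets up a test of a difference, and its nominal error rate assumes that grading does not favour a lens. Disclosure does not secure that.

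A second reply is that masking might fail anyway. The lenses differ in material, base curve (8.8 against 8.7 mm) and diameter (14.4 against 14.5), final powers may differ, and at Visit 1 both identified lenses are fitted and graded. This also stands in part. The documents do not show whether a grader can tell the lenses apart on the eye, so the benefit is likely but not established. One consequence is that Visit 1 grades and powers cannot be withheld from an investigator who ran Visit 1, and demanding it would mean a second trained grader. The fix below does not ask for it.

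Some stronger readings are tempting. A reader might infer that the grades will favour the test lens, but nothing in the documents shows a lean, its direction or its size. A reader might infer that the grader is certainly an unmasked investigator; section 4.1.3 and the slit-lamp setting point that way, but the grader is not named. A reader might infer that no other reason for leaving investigators unmasked exists, but parts of the protocol are redacted, so the statement covers the readable text only. And the 51% and 84% figures at SD 0.6 should not be quoted as the trial's risk, because that SD does not reproduce the plan's own sample size.

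**Conclusion.** The point holds as a design weakness that should be corrected. The primary comparison rests on a judgement grade whose assessor can know the lens, under an order in which lens and visit are fully confounded. A lean of 0.20 points, under half the 0.42-point target, would raise the false-positive rate from 5% to about 29%; a lean of 0.05 would raise it only to about 6%. These figures assume no true difference, a uniform net lean, 37 completers, a two-sided paired t-test and the back-solved SD of 0.84. They show how sensitive the test is to a lean, and they do not estimate the bias in this trial. If many grades are already 4, an upward lean is partly lost at the ceiling and the smaller rows apply.

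A reader might infer that randomising the order alone cures the problem. It does not: it removes the visit effect and the one stated obstacle to masking, and the lean is reduced only as far as the grader is actually masked.

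**What to change.** - **4.1.2:** randomise lens order, balanced between A-first and B-first (20 and 20 if all 40 places are used).
- **4.1.1, 4.4, 4.4.2, Table 2 and Table 3:** replace the lens labels on Visits 2 and 3 by *first study lens* and *second study lens*.
- **4.1.3:** replace the sentence on investigators with: *The person grading fit at V2 and V3 is not told which lens is worn. The assistant who prepares the unmarked case holds the order and the lens log until all V2 and V3 fit grades are recorded. The lens may be unmasked if needed to assess or manage an adverse event.* The binder entry in 4.3.4 ("All products dispensed to participants will be recorded in the study binder") should follow the same rule.
- **Visits 2 and 3:** record the grader's guess of the lens at each visit, so that the report can show how well masking held.
- **10.1:** add a comparison of lenses that accounts for order, for example the average of the A-first and B-first mean differences. With 37 completers this leaves 35 degrees of freedom instead of 36.
- **Section 12:** correct the status-report wording that treats being randomised as having been assigned a study ID.

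The same investigator may run Visit 1 and grade at Visits 2 and 3, so no second grader is needed. The cost is a randomisation list, form and label changes and the edits above, with no change to the sample size or the number of visits; the assistant already handles the lenses. The downside is that masking may be only partial, because of visible lens features, differing powers or recall from Visit 1. The recorded guess would reveal that but would not correct it.
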